6. HEALTH ECONOMICS

Aim

The objective of the health economics analysis is to assess the cost-effectiveness of different axSpA referral strategies, comparing strategies with current care and a comparison between strategies in a fully incremental analysis, applying the rules of simple and extended dominance. A cost-utility analysis will be undertaken to calculate cost per quality-adjusted life year (QALY) gained from an NHS perspective. NICE thresholds of £20,000/QALY and £30,000/QALY will be applied to the results.

Outcome measurement

The cost-effectiveness analysis will use pre-existing equations, as developed and advised by NICE 2017 clinical guideline for spondyloarthritis. This is specified in the section outlining the analysis approach. Outcome data required for the equations for each referral strategy will be available from WP2, namely the prevalence of the condition and test sensitivity and specificity. Data on quality of life is not required as this has already been factored into the model equations using utilities for health states.

Page 36 of 53
IDEAL BACKPACS Protocol Final Version 1.1 date 09-Oct-2024

Resource Use Measurement

Data on the health care resource use required for each referral strategy will be collected during WP2 (e.g., tests administered, or extra appointments required) costs calculated using standard NHS unit costs.

Analysis

As part of the development of latest NICE clinical guidelines in axSpA, a detailed model-based economic evaluation of axSpA referral strategies was constructed [3]. The Markov model, with a 3-month time cycle and lifetime time horizon estimated the costs and utility of being correctly identified with axSpA and being misdiagnosed and therefore being treated for chronic low back pain of unknown cause. The evaluation of a superior referral strategy included a complex interaction of the benefits, costs and harms associated with false-positive and false-negative diagnoses, with potential approaches trading off sensitivity and specificity. A key output of the model is two equations, one for discounted costs and one for discounted QALYs to allow assessment of the cost-effectiveness of future referral strategies, without researchers having to reconstruct the decision model. We therefore propose to use these equations in our analysis.

The equations are:

Costs = $\mathbf{C} + \mathbf{v} \mathbf{n} 107,307 + \mathbf{v} (1-\mathbf{n}) 104,966 + (1-\mathbf{v}) (1-\mathbf{p}) 559$

QALYs= vn14.571 + v(1-n)13.534

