
Where C is the initial cost of the strategy, v is the true prevalence of axSpA among people with chronic back pain of ≥ 3 months' duration with age of onset ≤ 45 , n is the sensitivity of the strategy and p is the specificity of the strategy.

The equation for the incremental cost-effectiveness ratio (ICER) versus current care (as specified in the NICE guidelines) is as follows:

ICER=
$$\underline{C} + vn107,307 + v(1-n)104,966 + (1-v)(1-p)559-5,264$$

 $vn14.571 + v(1-n)13.534-0.682$

The strategies for comparison will be the validated Baraliakos strategy, the alternative UK referral strategy (BACKPACS) and existing referral strategies assessed by the original NICE model.

Health economic uncertainty will be explored by changing the values of the equation variables to assess the robustness of the results. Due to the nature of the analysis with predetermined equations, probabilistic sensitivity analysis will not be undertaken, therefore Cost Effectiveness Acceptability Curves (CEACs) will not be presented.

Model development

The health economic model results will be used as part of the iterative process to design the 'superior' BACKPACS referral strategy. The initial estimates for Baraliakos and BACKPACS referral strategies will be entered into the equations and cost-effectiveness estimated. The effectiveness (specificity/sensitivity/likelihood ratio), cost-effectiveness estimates and feasibility (ease of implementation) will all be part of the package of information on the strategies provided to the CoP and PPI groups for discussion. Factors included in feasibility considerations would include variables that might be completed at a single GPC consultation (i.e., presence of buttock pain, previous history of enthesitis or uveitis), versus factors that would require further evaluation or clinic attendance (i.e., response to NSAIDs or blood test results (CRP / HLA-B27). Any changes to the BACKPACS strategy will then be factored into Page 37 of 53

IDEAL BACKPACS Protocol Final Version 1.1 date 09-Oct-2024

the analysis and results re-estimated. A number of cycles of statistical and health economic modelling and then CoP/PPI consideration may be required, before an eventual 'superior' referral strategy is determined.

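### Probabilistic sensitivity analysis is excluded because the equations are predetermined, yet their inputs are estimated in this study, so close cost-effectiveness rankings would carry no measure of decision uncertainty

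*Protocol*

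**What the plan says.** Section 6 of the protocol plans a cost-utility analysis that takes two closed-form equations, one for costs and one for QALYs, from the guideline's Markov model. The QALY equation is "QALYs= vn14.571 + v(1-n)13.534", where v is prevalence and n is sensitivity. The cost equation adds the strategy's initial cost C and a cost for false positives, which depends on specificity p.

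The inputs come largely from this study (work package 2, WP2). The outcome data "will be available from WP2, namely the prevalence of the condition and test sensitivity and specificity". For C, "Data on the health care resource use required for each referral strategy will be collected during WP2", priced with standard NHS unit costs.

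Strategies are compared with current care and with one another through "a comparison between strategies in a fully incremental analysis, applying the rules of simple and extended dominance", and "NICE thresholds of £20,000/QALY and £30,000/QALY will be applied to the results".

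On uncertainty, the plan says "Health economic uncertainty will be explored by changing the values of the equation variables to assess the robustness of the results". It then says "Due to the nature of the analysis with predetermined equations, probabilistic sensitivity analysis will not be undertaken", and draws the consequence that CEACs will not be presented.

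Under Model development in the same section, the economic results are among the information given to the professional and patient groups over repeated redesign cycles until a preferred strategy emerges.

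**The concern.** The predetermined part of the equations is their coefficients. That prevents the guideline model's own parameter uncertainty from being carried forward. It does not prevent sampling error in v, n, p and resource use from being carried through. These quantities are estimated here, on the same patients for every strategy.

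The protocol settles the matter and does not leave it open, so an analysis plan that follows it could not add a probabilistic analysis. The groups choosing between strategies would then see a net-benefit ordering, and a list of strategies ruled out by dominance, with no indication of how often another sample of the same size would reverse the order. This matters most for close pairs. The protocol expects the final choice to lie between the strategy under external validation and the new BACKPACS model, which is built partly from the same predictors.

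**Working it through.** **Size of the data.** Section 5.2 assumes N = 720, prevalence 14%, sensitivity 90% and specificity 65%. Cases: 0.14 × 720 ≈ 101. Non-cases: 619. The stated power of over 90% for lower bounds of 79% and 58% is reproduced with exact binomial tests at one-sided 5% (92.2% and 97.2%). The recruitment target also follows: 720/0.8 = 900. Simulated 95% sampling ranges at this size are 11.5 to 16.5% for v, 83.7 to 95.5% for n and 61.2 to 68.7% for p.

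**Value of accuracy in the equations.**
- QALYs per extra case detected: 14.571 − 13.534 = 1.037.
- Cost per extra case detected: 107,307 − 104,966 = £2,341.
- Net benefit per extra case detected at £20,000 per QALY: 20,000 × 1.037 − 2,341 = £18,399.
- Cost per false positive: £559.

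**A close pair.** The documents give neither the gap nor the agreement between strategies, so these are assumptions: sensitivities 3 points apart, equal specificity and C, 10% or 15% of cases discordant, 20% of non-cases discordant, v held at 0.14.
- Incremental QALYs: 0.14 × 0.03 × 1.037 = 0.0044.
- Incremental cost: 0.14 × 0.03 × 2,341 = £9.83.
- Incremental net benefit: 0.14 × 0.03 × 18,399 = £77.
- SE of the sensitivity difference at 10% discordance: √((0.10 − 0.03²)/101) = 0.0313. In money: 0.14 × 18,399 × 0.0313 ≈ £81.
- SE from specificity: 0.86 × 559 × √(0.20/619) ≈ £8.6.
- Combined SE ≈ £81, so Φ(77/81) = 0.83.
- At 15% discordance: √((0.15 − 0.03²)/101) = 0.0384, combined SE ≈ £99, so Φ(77/99) = 0.78.

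Sampling error in v adds little: 0.03 × 18,399 × √(0.14 × 0.86/720) ≈ £7, combined in quadrature with £81.

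**Published values.** Take the five Table 1 rows for the four existing strategies as true, assume equal C, and simulate 720 patients with an assumed latent within-patient correlation of 0, 0.5 or 0.8.
- At £20,000 the base-case best is the strategy under external validation (0.91/0.67), with net benefit £25,385 against £25,372 for the ASAS strategy. It stays best in 53 to 54% of draws; ASAS is best in 32 to 39%.
- At £30,000 the base-case best is ASAS, in 79 to 81% of draws.
- The base-case dominance frontier recurs in 71%, 77% and 84% of draws at the three correlations.
- For the strategy under validation against the modified ten-variable strategy (0.86/0.73), the probability that the former is preferred at £20,000 is 0.80 with independent errors and 0.97 under maximal dependence.

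**The anticipated final pair.** Compare 0.90/0.65 with two assumed BACKPACS results, again with equal C.

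| Assumed BACKPACS | Incremental net benefit at £20,000 | 95% interval, correlation 0 | 95% interval, correlation 0.8 |
|---|---|---|---|
| 0.88/0.70 | −£27 | −£256 to £194 | −£188 to £122 |
| 0.92/0.65 | £51 | −£156 to £259 | −£93 to £201 |

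**Feasibility.** In any sample vn is true positives divided by N, v(1−n) is false negatives divided by N, and (1−v)(1−p) is false positives divided by N. Costs and QALYs are therefore averages over participants, and resampling them jointly is simple.

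**Current care.** The protocol gives it only as £5,264 and 0.682 QALYs. In the same QALY equation 0.682 implies v between 0.682/14.571 = 0.047 and 0.682/13.534 = 0.050. At v = 0.14 even a strategy that detects nobody gives 0.14 × 13.534 = 1.895 QALYs. These constants cannot simply be carried into resamples at the study's v.

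**The case against.** A reader might infer more than the documents support.

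- **That the ranking rests on point estimates alone.** It does not. The equation inputs will be varied, and section 5.1 promises 95% confidence intervals for each strategy's accuracy and for comparative accuracy. Nor does the protocol say that inputs will be changed one at a time; multi-way variation, or values taken from confidence limits, would fit its wording.
- **That the close pair above shows dominance.** It does not. The more sensitive strategy costs more, at 2,341/1.037 ≈ £2,257 per QALY, which is an ordinary ICER. The plan will apply "applying the rules of simple and extended dominance", but extended dominance would need a third option that the illustration does not include.
- **That all four inputs are study estimates.** The unit costs within C are external.
- **That a dominated strategy is automatically dropped.** Cost-effectiveness is one of three kinds of information put to the groups, with effectiveness and feasibility.
- **That every ranking is noise.** The 0.97 under maximal dependence shows otherwise.

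It can also be said that a probabilistic analysis would barely move the expected ranking. The equations average over participants, so mean net benefit across resamples is essentially net benefit at the point estimates. That is correct, and it defines the gap: what is missing is a statement of decision uncertainty, not a correction of bias.

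These points narrow the concern but do not remove it. Neither input variation nor separate accuracy intervals yield a paired interval for incremental net benefit or a probability of being optimal, and the reason for leaving these out remains invalid.

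**Conclusion.** The stated justification is wrong and should not stand. With about 101 cases, strategies a few points apart in sensitivity would be ordered on a net-benefit difference about the size of its standard error: £77 against roughly £81 to £99, with probability 0.83 to 0.78 that the order is right. These figures rest on the assumed 3-point gap, the assumed discordance rates and equal C and specificity. The simulations also rest on assumed correlations and, for the new model, assumed accuracy. Wider gaps or stronger within-patient correlation would make rankings firmer, and the study's own paired data will show which case applies. Cost-effectiveness is a secondary objective, but it informs which strategy goes forward to implementation, so the change is worth making.

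**What to change.** Delete the sentence that gives predetermined equations as the reason, and replace the exclusion with a joint bootstrap of participants:

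1. In each resample re-estimate v and, for every strategy on the same resampled patients, n, p and resource use. Hold standard unit costs fixed and use optimism-corrected accuracy for BACKPACS.
2. Apply the fixed equations in each resample.
3. Report intervals for incremental net benefit between strategies, CEACs, and the probability that each strategy is optimal at £20,000 and £30,000 per QALY.
4. State that uncertainty in the guideline coefficients is not included, so the intervals are partial.
5. For current care, state an assumption for its cost and QALYs at the study's prevalence, or limit the probabilistic analysis to comparisons between strategies.

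The between-strategy part needs a short program and no new data, visits or participants. Current care needs an extra input or assumption that the protocol does not supply. The downside is that curves omitting coefficient uncertainty can look more precise than they are, which is why step 4 is needed.

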7. ADVERSE EVENTS

Reporting Requirements

The occurrence of an adverse event as a result of participation within this study is not expected and no adverse event data will be collected.

The risks of participating in this study are comparable to that of usual care. The clinical assessments are conceptually similar to what might have been done as part of usual practice. For example, participants may already be sent questionnaires about their condition and history before further clinical investigations take place. The clinical investigations in the study are all completed as per the NICE 2017 clinical guidelines for spondyloarthritis.

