3.2 Study Management

The roles and responsibilities for each organisation are documented in the Contractual Agreement and the responsibilities of the (Sponsor/CI/NCTU) specifically are detailed in the Delegation of Responsibilities agreement.

Chief Investigator

The Chief Investigator has overall responsibility for the study and shall oversee all study management. The data custodian will be the Chief Investigator.

Sponsor

University of Nottingham will undertake the role of Sponsor as defined by the UK Policy Framework for Health and Social Care Research 2017. Delegated responsibilities will be assigned to the Chief Investigator, participating NHS Trusts and Nottingham Clinical Trials Unit.

Trials Unit

The study is co-ordinated by the Nottingham Clinical Trials Unit (NCTU).

Programme Management Group

The Programme Management Group (PMG) will be responsible for the day-to-day management of the study. Membership includes (but is not limited to) the CI, Trial Manager, Trial Statistician and other members of the NCTU multidisciplinary team as appropriate. The PMG will ensure high quality study conduct, to time and within budget, monitor all aspects of the conduct and progress of the study, ensure that the protocol is adhered to and take appropriate action to safeguard participants and the quality of the study itself. The PMG will also be responsible for ensuring project milestones are achieved. The PMG will meet regularly during the entire course of the study.

Programme Steering Committee

A Programme Steering Committee (PSC) will be established which includes an independent chair, independent and non-independent members and patient representatives. The role of the PSC is to provide oversight of the study. A meeting will take place approximately 6 months then 18 months after the first participant is recruited with all meetings thereafter taking place approximately every six months during the recruitment phase of the study.

PSC members will be asked to sign the IDEAL PSC Charter which will outline their roles and responsibilities. The PSC will consider and act, as appropriate in accordance with the PSC Charter, and ultimately carries the responsibility for deciding whether the study needs to be stopped on the grounds of safety or efficacy.

Data Monitoring Committee

There will be no separate Data Monitoring Committee (DMC) formed for this project as no safety data is being collected. The PSC will act in accordance with the PSC charter and

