		and Leeds Enthesitis Index (LEI)
		16 sites assessed in total: the greater trochanter, quadriceps tendon insertion into the patella, patellar ligament insertion into the patella and tibial tuberosity, Achilles tendon insertion, plantar fascia insertion, medial and lateral epicondyles, and the supraspinatus insertion. Presence or absence of tenderness; max
		score = 16
Mobility	Bath Ankylosing Spondylitis Metrology Index (BASMI)	Index comprising 5 measures of spinal and hip mobility
Personal history	 a. Onset of chronic back pain symptoms b. Dactylitis c. Enthesitis d. Skin/nail psoriasis, e. Colitis f. Uveitis g. Anterior chest pain 	Self-reported, current and previous
Family history	Presence in first degree or second- degree relatives* of any of the following: a. Skin/nail psoriasis b. Colitis c. Uveitis, d. axSpA, e. Reactive arthritis, f. PsA	Self-reported (yes/no) and number of relatives affected
Response to NSAIDs	Only if NSAID response is not completely clear. At least one week at max tolerated dose. (If NSAID response if not completely clear) for individuals with no contraindications, min 7-day course of full dose NSAIDs (with telephone evaluation of NSAID response from research team at 1 week)	Self-reported (yes/no)

Page 30 of 53 IDEAL BACKPACS Protocol Final Version 1.1 date 09-Oct-2024

Blood tests	Blood tests			
Diagnostic laboratory tests	HLA-B27	Positive testing according to standard laboratory techniques.		
	CRP	C-reactive protein above upper normal limit in the presence of back pain, after exclusion of other causes for elevated CRP concentration.		
Imaging				
x-ray	Conventional SIJ plain x-rays	Modified New York criteria for each SIJ		
MRI	SIJ and whole spine (30 min scan) arranged within 4 weeks** of clinical assessment.	 (i) Description of oedema and structural features (fat metaplasia, erosions, ankylosis) in SIJs – yes/no for each. Interpretation according to ASAS specifications (bone marrow oedema in typical location 'highly suggestive' of axSpA) - yes/no for MRI positivity (ii) Are there unequivocal features of spinal inflammation? (yes/no) (iii) Overall impression across x-ray and MRI – (a) normal (b) equivocal (c) axSpA (d) other 		

^{*}First degree relative includes an individual's parents, siblings and children. Second degree relative includes grandparent, grandchild, half siblings, aunt/uncle and niece/nephew. **where possible, waiting times may vary between sites.

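### Section 7 rules out collecting adverse event data, so intolerance of, or a serious reaction to, the conditional NSAID course in Table 6 would not be systematically recorded

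*Protocol*

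**What the plan says.** Section 7 sets one rule for the whole study: an adverse event arising from participation "is not expected and no adverse event data will be collected". The stated ground is that "The risks of participating in this study are comparable to that of usual care". The section supports this by saying that "The clinical assessments are conceptually similar to what might have been done as part of usual practice", by giving questionnaires as an example, and by stating that the clinical investigations follow the 2017 NICE guideline. It names no drug.

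Section 3.2 repeats the position. There will be "no separate Data Monitoring Committee (DMC) formed for this project as no safety data is being collected". The same section makes the PSC ultimately responsible for deciding whether to stop the study on safety or efficacy grounds.

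Table 6 in section 4.1.4 has a row for response to NSAIDs, placed under the clinical assessment heading. It applies "Only if NSAID response is not completely clear. At least one week at max tolerated dose", and it directs, "for individuals with no contraindications, min 7-day course of full dose NSAIDs", "with telephone evaluation of NSAID response from research team at 1 week". The table defines the feature as a yes/no self-report. The course does not appear in the synopsis description of interventions or in the assessment schedule in Table 4.

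**The concern.** The rationale in section 7 is illustrated entirely by assessments, questionnaires and investigations. The NSAID course is different in kind: the protocol directs some participants to take a drug for a week, and the research team follows it up. A participant might stop early because of intolerance, or might have a serious reaction. The protocol provides for a conversation at the right moment, but specifies only a question about response.

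What is at stake is participant safety oversight. The PSC holds the decision to stop on safety grounds, yet under the stated rule it would have no routine information about the one drug course that the study itself directs. Whether adverse events are collected is a matter for the protocol, and this protocol answers it expressly, so the point cannot be left to the statistical analysis plan.

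**Working it through.** No figure is in dispute and no arithmetic applies. The check sets the relevant parts of the protocol side by side.

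**1. Is there a study-directed drug exposure?** Yes, a conditional one. Table 6 sets three limits: response must be unclear, there must be no contraindication, and the dose is the maximum tolerated. Within those limits it directs at least 7 days at full dose.

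**2. Does section 7 deal with it?** Only through its general statement that risks match usual care. Neither the course nor any medicine is mentioned.

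**3. Does the specified contact capture reactions?** The one-week call is specified to evaluate response, and the feature is defined as a yes/no self-report of response. Nothing in the row asks about intolerance or a serious reaction, and section 7 says such data will not be collected.

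**4. Does another route capture them?** Each candidate was read in turn.

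| Section | What it provides | Does it systematically record a drug reaction? |
|---|---|---|
| 3.2 | Independent PSC members can act as a data monitoring committee if the need arises | No. No stated data flow would show the need |
| 3.4.4 | Reasons for withdrawal are requested | No. Answering is optional, and stopping tablets is not withdrawal |
| 4.1.6 | Reports entered on the database include diagnoses of serious conditions | No. This concerns diagnostic findings |
| 4.2.4 | Compliance with study procedures is monitored through the database | No. It may cover whether the course was completed, but not reactions |
| 4.2.5 | The Programme Management Group and the PSC receive progress updates | No safety content is stated |
| 9.3 | Data checks, triggered monitoring, and possible reporting of major problems to the PSC and ethics committee | No. Reporting is discretionary and relies on data that section 7 says are not collected |
| 9.6 | Disclosed risk of harm is discussed with the chief investigator | No. It depends on someone volunteering the information |

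**5. How many people are affected?** The protocol does not say how many participants would have an unclear NSAID response and be free of contraindications. The number exposed cannot be derived, and no estimate is offered.

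The result is several partial routes, none of which would systematically record intolerance of the course or a serious reaction to it.

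**The case against.** The strongest reply is that the protocol is consistent and its premise is reasonable. Sections 3.2 and 7 agree with each other. The NSAID row sits under clinical assessment, and section 7 describes the clinical assessments as similar to usual practice, so the course arguably falls within the stated rationale without being named. NSAID response is an element of the Baraliakos, modified Braun and ASAS strategies in Table 3. Section 1.2 recognises that assessing it needs clinical follow-up, and section 4.1.5 expects some participants to be taking NSAIDs already. On this view, naming the course and adding a question is drafting preference.

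Much of this stands. A reader might infer that the course is riskier than usual care, or that the protocol contradicts itself. The documents support neither. What remains is that comparable risk is not zero risk: the study directs this course and follows it up, while an express rule excludes any record of harm from it.

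A second reply is that the last column of Table 6 defines a feature and is not the call script or the electronic case report form, which are not shown. This also stands. A reader might conclude from the table that completion of the course goes unrecorded. That does not follow, because section 4.2.4 provides for compliance to be monitored through the database. The point therefore rests on reactions alone, where section 7 is explicit.

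A third reply is that the PSC works under a charter that is not shown, and that the stopping phrase is general oversight wording. That is fair, and the phrase does not by itself require adverse event collection. But a charter cannot bring routinely to the committee data that the protocol says are not collected.

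**Conclusion.** The point holds as a minor one. Under the stated rule, intolerance of, or a serious reaction to, the conditional NSAID course would not be systematically recorded and would not routinely reach the PSC. This rests on reading section 7 as it is written and on Table 6 being the protocol's specification of the one-week call. If the call script already asks about reactions, section 7 and section 3.2 are wrong as worded and need the same correction.

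The size is limited by the short duration, the three conditions on the course and the unknown number exposed. A reader might also wonder whether the study's results are at risk. They are not: accuracy estimates, the reference standard and the sample size do not depend on this.

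**What to change.** Name the NSAID course in section 7 as an exception to the rule. At the existing one-week call, record whether the course was stopped early and why, with intolerance as an explicit reason, and record any serious event. Report serious events to the sponsor and give the PSC a brief summary. Amend the statement in section 3.2 that safety data are not collected, so that it agrees. Section 7 can stay as it is for questionnaires, examination, blood tests and imaging.

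The cost is a short protocol amendment, a few extra fields in the electronic case report form and a brief committee summary. No new visit or call is needed.
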